**BACKGROUND AND RATIONALE**

**Osteoarthritis (OA):**

Osteoarthritis (OA) is the most common type of joint disease, affecting more than 30 million individuals in the United States alone [1]. It is the leading cause of chronic disability in older adults, costing the US greater than \$185 billion annually [2]. Some people call it degenerative joint disease or “wear and tear” arthritis. It occurs most frequently in the hands, hips, ankles and knees. With OA, the cartilage within a joint begins to break down and the underlying bone begins to change. These changes usually develop slowly and get worse over time. OA can cause pain, stiffness, and swelling. In some cases, it also causes reduced function and disability; some people are no longer able to do daily tasks or work. Current treatments include intra-articular oral pharmacologic, Nonsteroidal anti-inflammatory drugs (NSAIDs), corticosteroid injections, and arthroplasty (partial or full joint replacement).

The progression of osteoarthritis has been divided into three stages including proteolytic breakdown of cartilage, fibrillation and erosion of cartilage surface with release of proteoglycan and collagen fragments into the synovial fluid, and cartilage breakdown inducing a chronic inflammatory response in the synovium, creating further cartilage breakdown.

We are interested in the clinical effects of human amniotic fluid’s natural anti-inflammatory, immunomodulatory and growth-promoting properties to reduce and/or eliminate the inflammatory cascade of events leading to the degradation of cartilage; as well as, the possibility of using AF as an alternative to current treatments that can have a long-term detrimental effect on tissues such as corticosteroids.

**Amniotic fluid (AF): Preclinical Data**

Early after conception and until the mother’s water breaks for the delivery of their infant, the fetus is bathed in amniotic fluid. AF functions as a supportive cushion to the fetus and provides a protective environment. AF is a rich source of nutrients, cytokines and growth factors that are required for fetal development and maturation [3]. AF also contains stem cells with the potential to differentiate along multiple cell lineages [4, 5]. The protective and regenerative properties of AF are achieved via the exchange of water and solutes with surrounding tissues. This is accomplished via the utilization of

**A Phase I/II Randomized, Double-Blinded Standard of Care (Corticosteroid vs Sterile Amniotic Fluid for Osteoarthritis**

**PI: [name].**

**Version: 5.00 dated 23MAY2023**

different pathways during the course of a pregnancy that likely contribute to changes in the composition of the AF with gestational age [3].

A report that concentrates of AF inhibited the development of peritonitis was among some of the first evidence that AF had protective biological properties [6]. This was followed by a publication by Shimberg and co-workers that AF accelerates defense-repair mechanisms within damaged joints [6, 7]. Since these early publications, more sophisticated evaluations have revealed the presence of antimicrobial, immunomodulatory, and growth-promoting activities in AF [3]. Reports about antimicrobial activity in AF differ [8] among investigators. Some studies show that AF is inhibitory, while others show no effect against the same microorganisms. Yet, others show evidence that AF with low antimicrobial activity is associated with a high incidence of an infectious syndrome in pregnant women [9]. Components with antimicrobial, antiviral and antifungal activity that are present in AF include lysozyme, peroxidase, transferrin,  $\beta$ -lysin, immunoglobulins and zinc-peptide complexes [8], just to name a few.

Immunomodulatory properties of AF are evident from studies showing that enteral feeding of AF suppresses the pro-inflammatory responses in preterm pigs with necrotizing enterocolitis [9]. While growth promoting activities of AF are supported by animal studies as well as by in vitro studies showing that AF can enhance neochondrogenesis [10], regenerate peripheral nerves [11] and bone [12], accelerate re-epithelialization in corneas [13], and promote healing of human skin wounds [14]. Some of the factors that are found in AF that may contribute to these activities include inflammatory mediators that include, but are not limited to TNF- $\alpha$ , IL-6, IL8, and IL-10 [15], trophic factors that include EGF, IGF-1, FGF, HGF and TGF- $\alpha$  [16-17], and HA, an important factor in promoting re- epithelialization in human skin wounds [14].

Based on the hypothesis that nutrients, cytokines and growth factors contained in the non-cellular fraction of AF are useful for reparative and regenerative treatments in patients, [name] et al., conducted a study at the University of Utah to address three issues. The first was to determine the feasibility of consenting and screening volunteer donors for the routine collection of AF from full-term pregnant women scheduled for caesarean- section (C-sections) and then processing the AF for clinical applications. The second aim was to develop a processing method that resulted in a cell-free AF preparation suitable for clinical applications. The third goal was to gain a better understanding about components of AF procured from full-term pregnancies.

With the above 3 goals in mind, human AF was collected by the staff of the Obstetrical and Gynecological department at the University of Utah hospital and was processed by technical staff of the Cell Therapy and Regenerative Medicine (CTRM) facility at the University of Utah. Physician executed abdominal incisions were performed through the abdominal and uterine muscles without cutting into the amnion membrane. Using a sterile soft suction catheter connected to a sterile MediVac Suction Container (Cardinal Health, Waukegan, IL), a blunt end insertion with a catheter was made into the amnion membrane and the AF was aseptically suctioned into a MediVac Container. The container was labelled, wrapped in frozen Insul-ice mats (Fisher Scientific, Hanover Park, IL) and placed in a temperature-monitored shipper that was validated for transport between 2 and 8 °C. The AF was transported to the Cell Therapy and Regenerative Medicine (CTRM) facility at the University of Utah. Upon arrival at the CTRM facility, the product was immediately placed into a refrigerator at 2–8 °C until

## **A Phase I/II Randomized, Double-Blinded Standard of Care (Corticosteroid vs Sterile Amniotic Fluid for Osteoarthritis**

**PI: [name].**

**Version: 5.00 dated 23MAY2023**

processing occurred. At the time of processing, the MediVac container with AF was aseptically placed in a biological safety cabinet and the AF was transferred via aseptic techniques into sterile centrifuge tubes. The total volume and gross appearance of the AF were recorded and samples were removed for sterility testing, cell counts and other relevant testing. The AF was centrifuged at 1400Xg for 20 min at 4 °C. Once centrifugation was complete, the supernatant was expressed into a new transfer pack and the remaining cell pellet was characterized and cultured as described below. The supernatant from the AF was processed using a proprietary filtration technology to sterilize and eliminate cellular debris from the final product. AF collections and final products were evaluated for total volume, fluid chemistries, total protein, and hyaluronic acid (HA) levels. Final products of processed AF (pAF) were also assessed for their cellular content and for their protein profiles using quantitative antibody arrays.

To validate the above described approach for collecting and processing AF, 36 pregnant women consented and passed the donor screening criteria. AF was successfully collected from 17 individuals. Median AF volumes were 70 mL (range 10–815 mL; n = 17). Fluid chemistries were similar, but some differences were noted in HA levels and cytokine profiles. Cytokine arrays revealed that an average of  $304 \pm 20$  (mean  $\pm$ SD; n=3) of 400 proteins tested were present in AF with a majority of cytokines associated with host defense. Some of the peptides encountered and classified according to their function are found on **Table 1**.

**Table 1**

Pro-inflammatory	OPN, PAI-I, CD163, RAGE, IL17, IL1R3
Host defense	IL-27, LAG-3, GITR, PD1
Innate Immunity	hCGb, Galectin-3, TLR-2, Osteoactivin
Antimicrobial	TSP-1, lactoferrin, CXCL14, Trappin-2, CCL-28, MIG
Anti-inflammatory	IL1-ra, MBL
Embryonic development	DKK1, DKK3
Angiogenesis	VEGF R1, Transferring, TIMP-2
Wound healing	OPN, PAPP-A, FAP

**ELIGIBILITY CRITERIA**

Eligible participants will be identified by study staff.

**Inclusion criteria are:**

1. Age between 18-75 years; AND
2. Confirmed diagnosis of knee osteoarthritis based on clinical and radiographic findings consistent with Kellgren-Lawrence Stage 2-3 disease; AND
3. Patients who have failed conservative treatment (e.g. steroid, activity modification, therapy, etc.) within 3 months; AND
4. Unilateral or bilateral chronic knee joint pain >4 months; AND
5. Must be able to ambulate (not wheelchair bound); AND
6. Patient reported a typical pain of at least 4 out of 10 during the past week using VAS numeric pain scale (0-10)

**Exclusion criteria are:**

1. Subjects who have had a previous injection (steroid, Platelet Rich Plasma (PRP), or other) within the last 3 months; OR
2. BMI > 40 as defined by NIH Clinical Guidelines Body Mass Index; OR
3. Concurrent participation in another investigational trial involving systemic administration of agents (within the previous 30 days) or plans to participate in any other allogeneic stem cell therapy trial during the 12 month follow-up period; OR
4. Clinical suspicion of infection at injection site; OR
5. Any surgeries within 4 weeks, other than diagnostic surgery; OR
6. Insulin or self-reported non-insulin dependent diabetic evident of HgA1c  $\geq 8\%$  among known diabetics; OR
7. Unable to consent to an English Language Consent Form; OR
8. Frank mechanical issues (i.e. locking of the knee); OR
9. Workman's Compensation cases; OR
10. Rheumatoid arthritis; OR
11. Patients with a known allergy to local anesthetics or components of the study drug (pAF or steroid injection); OR
12. Patients with vascular claudication or neurologic disorders affecting the index lower limb; OR
13. Patients with inflammatory arthropathies or connective tissue disorders; OR

**A Phase I/II Randomized, Double-Blinded Standard of Care (Corticosteroid vs Sterile Amniotic Fluid for Osteoarthritis**

**PI: [name].**

**Version: 5.00 dated 23MAY2023**

14. Patients with known alcohol or drug abuse or dependence, recreational use of illicit drug or prescription medications, or have used medical marijuana within 7 days of study enrollment; OR
15. Patients with history of active cancer/malignancy within 2 years of screening, apart from adequately treated basal cell or squamous cell carcinoma of the skin not associated with the target knee; OR
16. Women who are nursing or pregnant; OR
17. Patients of childbearing potential who are unwilling to use adequate contraception for 90 days after study drug injection.

**OVERALL STUDY DESIGN**

The blinded standard of care-steroid injection (SOC) vs. amniotic fluid injection (pAF) to treat and reduce osteoarthritis (OA) inflammation and pain will consist of 60 patients, wherein half of the patients will be in the SOC treatment arm and half of the patients will be in the AF arm. The PI ([name]) and patients will be blinded as to the arm in which they will be participating.

**Screening and Enrollment**

Patients will be screened and consented at the University of Utah Orthopedic Center and all participating sub-investigator's clinics when they come for a standard of care physical exam. During this exam, the patient will be asked about their health and lifestyle, medical history, and current medications. As part of the SOC physical exam, the patient will also have standard of care pre-treatment x-rays, neurological assessment, and a diagnosis of mild to severe OA in the knee joint assessment. The patient will also complete standard of care questionnaires including pain assessment and outcome surveys which are described below:

- Pain will be measured by the Visual Analog Scale for pain (VAS Pain). VAS Pain is a patient-reported measurement tool used to quantify perceived level of pain, graded on a scale from 0 to 10 with 0 representing no pain and 10 representing the worse pain possible, and with precise measurement of the marked pain level's distance from 0 comprising the pain level.
- Functional outcomes will be assessed using Single Assessment Numerical Evaluation (SANE), PROMIS Physical Function CAT (PF CAT), and Knee Injury and Osteoarthritis Outcome Score (KOOS) scoring scales.
  - The SANE asks the patient to evaluate their percentage of normal on the affected joint or region of interest. This is a one-question survey with a scale from 0-100%.
  - The PFCAT is a bank of 160 questions related to physical function. It is a computerized adaptive test that asks the patient to self-report capabilities rather than actual performance of physical activities. It includes functioning of upper extremities, lower extremities, and central regions. It also assesses instrumental activities of daily living, such as running errands.

**A Phase I/II Randomized, Double-Blinded Standard of Care (Corticosteroid vs Sterile Amniotic Fluid for Osteoarthritis**

**PI: [name].**

**Version: 5.00 dated 23MAY2023**

- The KOOS is a survey with 42 questions that assesses joint symptoms, pain, pain during daily activities, physical function in daily living, as well as physical function during sports or recreational activities. It also assesses quality of life.
- Review of systems questionnaire (will only be completed during the 3, 6, and 12 months follow up period).

If the patient is found to be eligible for the study, research staff will approach the patient for informed consent. Patients with bi-lateral knee OA can participate but only one knee will receive the study treatment. The treating physician/principal investigator and the patient will discuss which knee should be treated with a study injection. Patients who have bi-lateral knee pain will need to consent that only one knee will be treated with study injection and are willing to forego steroid injection in the non-target knee for the duration of the study. Those who have previously undergone steroid injection will have to wait 3 months after last injection before participating in the study. Medications, such as anti-inflammatories, pain relievers, etc. may be used throughout the duration of the study and will be recorded as concomitant medications throughout the study period and at each follow-up visit.

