**Exploratory Endpoints**

- Number of treatment emergent adverse events (AEs) directly related to the injection. [Time Frame: 1 day, 2 days, 1 month, 3 months, 6 months and 12 months]
- Pain level following the injection based on Visual Analog Scale scoring. [Time Frames: 1, 3, 6 and 12 months]
- Functional outcomes scoring using Single Assessment Numerical Evaluation (SANE), PROMIS Physical Function CAT (PF CAT), and Knee Injury and Osteoarthritis Outcome Score (KOOS) scoring scales. [Time Frames: 1, 3, 6 and 12 months]

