**A Phase I/II Randomized, Double-Blinded Standard of Care (Corticosteroid vs Sterile Amniotic Fluid for Osteoarthritis)**

**PI: [name].**

**Version: 5.00 dated 23MAY2023**

**PATIENT STUDY CALENDAR**

	Screening /Baseline	Day 1 (24± 5 hours post injection)	Day 2 (48 ± 5 hours post injection)	1-Month (± 1 week)	3-Months (± 2 weeks)	6-Months (± 1 month)	12-Months (± 1 month)	As needed
Eligibility A	X							
Informed Consent	X							
Medical History	X							
Concomitant Medications	X			X	X	X	X	X
Physical Exam	X			X				X
Laboratory tests B	x							
Randomization	X							
Study Drug Administration	X							
Follow-up Contact C		X	X	X D	X	X	X	X
In Person Follow-up Visit				X D				X
Pain Assessment E	X			X	X	X	X	
Outcome Assessment F	X			X	X	X	X	
Review of systems questionnaire G					X	X	X	
Review of adverse events H		X	X	X	X	X	X	X
Knee Aspiration I	X							
Aspiration Characteristics J	X							

B Laboratory tests include: PT/INR (only applicable to patients taking blood thinners) and urine hCG (only applicable to women of childbearing potential)

C Follow up Email/phone call/text may occur to clarify any responses and/ or assess AEs and/ or establish contact with the patient.

D The patient may receive a phone call by the study team to do remote clinic visit and complete questionnaires if the patient is unable to return to clinic to do in-person visit.

E Visual Analog Scale (VAS).

F Single Assessment Numerical Evaluation (SANE), PROMIS Physical Function CAT (PF CAT), and Knee Injury and Osteoarthritis Outcome Scale (KOOS). These surveys may be sent via email/text or done over the phone.

G This questionnaire may be sent via email/text or done over the phone.

H The study team may call the participant to assess adverse events in between the scheduled follow-up visit and phone calls.

I If deemed applicable by the treating provider.

J Only applicable if there is a suspicion of infection as determined by the treating provider.

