**DATA COLLECTION**

Patients will be evaluated at baseline in the clinic. At 1 month after the injection an in-person clinic follow-up visit will occur. At this visit, concomitant medications, pain assessment, and outcomes will be assessed, as well as a physical exam and review of adverse events. Three, six and twelve months post injection, research staff will send an email/text to patients with a link to the surveys. If patients do not complete surveys within a week, research staff will follow up with a phone call to the patients inquiring about their knee(s) and instruct them to complete the various assessment tools online (VAS, SANE, PFCAT, and KOOS). Research staff may call patients after they complete surveys to clarify any responses. Information about repeat injections will be collected, including date of injection. Additional visits, which include a physical exam, review of concomitant medications and adverse events, will be done as needed.

Medical history, concomitant medications and physical exam will be collected at the baseline visit, prior to randomization. Concomitant medications will also be collected at the following time points: 1, 3, 6 and 12 months. Adverse events will also be collected at all follow-up time points (1 day, 2 days, 1 month, 3 months, 6 months and 12 months after baseline).

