**Data Collection Procedures for Adverse Events**

After patient randomization all adverse events (including serious adverse events) will be recorded according to relatedness, severity, and expectedness, as well as their duration and any treatment prescribed. Any medical condition present at the time of randomization, recorded in the patient's baseline history at study entry, which remains unchanged or improves (unless the clinician feels it is clinically relevant), will not be recorded as an adverse event at subsequent evaluations. However, worsening of a medical condition that was present at the time of randomization will be considered a new adverse event and reported.

Adverse events will be coded using the MedDRA coding vocabulary. Coding will be done centrally at the Data Coordinating Center as this requires specific training.

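### The review-of-systems questionnaire has no pre-randomization administration, so symptoms missed by the baseline history may be recorded as new adverse events

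*Combined protocol and SAP*

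**What the plan says.** The form appears in the list of questionnaires under Screening and Enrollment, but with a restriction: "Review of systems questionnaire (will only be completed during the 3, 6, and 12 months follow up period". In the Patient Study Calendar, the row "Review of systems questionnaire" is marked at 3, 6 and 12 months and is blank at Screening/Baseline, Day 1, Day 2 and 1 month.

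Baseline health is gathered by other means. At the screening exam "the patient will be asked about their health and lifestyle, medical history, and current medications", and the same section adds x-rays and a neurological assessment. The Data Collection section states: "Medical history, concomitant medications and physical exam will be collected at the baseline visit, prior to randomization". VAS, SANE, PF CAT and KOOS are also completed at baseline.

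The section on data collection procedures for adverse events sets the before-and-after rule. The exemption covers "Any medical condition present at the time of randomization, recorded in the patient's baseline history at study entry, which remains unchanged or improves", with an exception where the clinician finds the condition clinically relevant. In the other direction, "worsening of a medical condition that was present at the time of randomization will be considered a new adverse event and reported". The adverse event endpoint, listed as exploratory, is "Number of treatment emergent adverse events (AEs) directly related to the injection".

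**The concern.** Whether a symptom counts as an adverse event depends on what was known about it at randomization. From month 3 the trial asks about symptoms with an instrument that it did not use at baseline. A long-standing complaint can go unmentioned in the history and then be reported when the form asks about it. It then has no baseline entry to exempt it, and no earlier answer to show whether it is stable or worse.

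This matters because safety of pAF is the first primary objective in the Synopsis, and the absolute adverse event experience of about 30 pAF participants is the evidence for it. The DSMB also reviews all adverse events at its scheduled meetings, not only related ones. A baseline answer cannot be reliably recovered after treatment.

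**Working it through.** The plan gives no figure on this point, so the main check sets its sections side by side. Its only design calculation is the power for repeat injection (50% against 10%, 30 per arm, alpha 0.05). Exact enumeration of the two-sided Fisher test gives 0.914, against about 90% stated. That figure reproduces and is not affected by this point.

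**Step 1: what is asked, and when** (Patient Study Calendar, Screening and Enrollment, Data Collection).

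| Source | Screening/Baseline | 1 month | 3, 6, 12 months |
|---|---|---|---|
| Medical history | yes | no | no |
| Physical exam | yes | yes | only as needed |
| Concomitant medications | yes | yes | yes |
| VAS, SANE, PF CAT, KOOS | yes | yes | yes |
| Review-of-systems form | no | no | yes |
| Adverse event review | no | yes (also days 1 and 2) | yes |

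The review-of-systems form is the only questionnaire used at follow-up that has no baseline counterpart.

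**Step 2: apply the adverse event rule to a symptom reported on the form at month 3.**

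- In the baseline history and unchanged or improved: not recorded, unless clinically relevant.
- In the baseline history and worse: recorded, but the change must be judged without an earlier answer on the same form.
- Present before randomization, not in the history, unchanged: the exemption requires a baseline record, so it does not apply, and the symptom may be recorded as new.
- New since randomization: recorded, correctly.

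On the form alone, the third and fourth cases look the same.

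**Step 3: which counts are exposed.** The general listing takes all events from randomization to 12 months and has no relatedness filter. The exploratory endpoint counts only events directly related to the injection, and an investigator must judge relatedness, so it is less exposed. It is not fully protected: an event with compatible timing can be classed as possibly related even if other factors could explain it, and the plan does not say which of its relatedness categories count as directly related.

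**Step 4: direction.** The form is given on the same schedule in both arms, and patients and treating physicians are blinded. Missed baseline symptoms should therefore arise at the same expected rate in each arm, adding to counts and to noise without favouring either.

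**Step 5: size, by assumption only.** Let q be the proportion of participants with a symptom that the baseline history missed and the form later elicits. The documents do not give q. Participants open to the error number 30 × q per arm and 60 × q overall.

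| Assumed q | Per arm | Overall |
|---|---|---|
| 5% | 30 × 0.05 = 1.5 | 60 × 0.05 = 3 |
| 10% | 3 | 6 |
| 20% | 6 | 12 |
| 30% | 9 | 18 |

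These are participants for whom the error could occur before anyone checks the answer. They are not predicted adverse event rates.

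**The case against.** The strongest reply is that the link from form to adverse event is assumed. No section says that review-of-systems answers become adverse event records, adverse event review is a separate calendar row, and the items on the form are not given. This stands as a limit on what can be claimed. It also shows a gap: nothing requires the answers to be checked against the history, and treatment emergent is not defined.

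Second, baseline is more than a bare history. It includes medications, a physical exam and a neurological assessment, and KOOS and VAS already score symptoms and pain in the target knee. Staff may also call to clarify answers, and adverse events are reviewed at days 1 and 2 and month 1. These points stand and narrow the exposure to symptoms that all of these sources missed. The clarifying calls are optional, however, and no physical exam is scheduled after month 1.

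Third, the timing may be deliberate, with the form taking the place of an exam at the remote contacts. That is plausible and would make a baseline form an improvement, not the repair of a contradiction.

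A reader might go further and infer that the pAF adverse event rate is inflated by a known amount, or that a misdated symptom would suspend the trial under the stopping criteria. The documents support neither. They give no rate of missed symptoms and no true adverse event rate to add it to. The relevant stopping criterion needs an event that is both severe and possibly or probably related, and severe events are described as usually potentially life-threatening or incapacitating. A stable complaint too minor to mention at baseline is an unlikely trigger.

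**Conclusion.** The timing gap is certain: the text and the calendar agree that the form is never given before treatment. The consequence is conditional. It requires a symptom that the history and exam missed, that the form later elicits, and that is then recorded without its onset being established. Under those conditions absolute adverse event counts may be inflated and noisier, and worsening lacks a like-for-like reference.

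The size is unknown. The range of 1.5 to 9 participants per arm is arithmetic on an assumed 5% to 30%. Nothing here supports a directional bias between arms or affects the primary efficacy comparison. This is an inexpensive improvement to the interpretability of the absolute pAF safety data.

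**What to change.** 1. Mark the review-of-systems questionnaire at Screening/Baseline in the Patient Study Calendar, and delete the word that restricts it to follow-up in Screening and Enrollment.
2. State that it is completed before randomization. Before injection is not enough: adverse events count from randomization, and randomization may take place at the initial visit, ahead of the injection day. A form completed in between could turn a reportable event into a baseline condition. The calendar column alone does not settle the order, because it also contains randomization and study drug administration.
3. State that answers at 3, 6 and 12 months are compared with the baseline form and the baseline history, under the existing rule for pre-existing and worsened conditions and with its clinical-relevance exception kept, before they are recorded as adverse events.

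The cost is a few minutes per participant at a visit where four questionnaires are already completed, plus the calendar and text edits. There is no added visit and no change to the sample size or the tests. For anyone randomized before the change takes effect, the comparison would rest on the history and exam alone, and the report should say so.
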